#### **Questionnaire-assessed child psychopathology, prenatal factors and pubertal development, self-report psychopathology**

The main-caregiver will provide information on the child and their environment, including:

1. Family size and structure, social class, pregnancy and childbirth (age at birth, birth weight, ante- and perinatal health problems, smoking and alcohol use, as collected by the modified Lewis scale).
2. Life Events Checklist to screen for possible traumatic events experienced by the child (Johnson et al., 1980).
3. Family relationship quality i.e. overall family relationship quality (Family Environment Scale; Moos et al., 2013) and parent child relationship quality (warmth and hostility)(Iowa Family Interaction Rating Scales; Melby et al., 1997).
4. Child prosocial and antisocial behaviour, ADHD and emotional symptoms by completing the Strengths and Difficulties Questionnaire (SDQ; Goodman et al., 2011).
5. Child development and behavioural problems with the Developmental Behaviour Checklist (DBC; Einfeld et al., 2002) which was developed specifically for children with intellectual disability and will not be completed for the unaffected siblings.
6. The Social Communication Questionnaire (SCQ; formerly Autism Screening Questionnaire (ASQ); Berument et al., 1999) will be used to screen for autism.

7. Child pubertal development will be obtained by Peterson assessment (Peterson, 1988).
8. Physical activity and Development Coordination Disorder using the Development Coordination Disorder Questionnaire (DCDQ; Wilson et al., 2009) and the Children's Physical Activity Questionnaire (cPAQ) (Corder, 2009)
9. Repetitive Behavior Scale Revised (RBSR; Bodfish et al., 2000)
10. Child eating style and behaviour, with the Child Eating Behaviour Questionnaire (CEBQ; Carnell et al, 2007)) and the Hyperphagia Questionnaire (HQ) (Fehnel, 2015).
11. Epilepsy and seizures using the Epilepsy screening questionnaire (Ottman et al., 2010).
12. Record of medication, operations, contact details of GP, school and screening questions about current state of health.
14. Identify the presence and severity of social impairment using the Social Responsiveness Scale, 2nd Edition (SRS-2; Constantino et al., 2005)
15. Screening for eating disorders: a) anorexia nervosa and bulimia using the Eating Disorder Examination (self-rated) Adolescent Questionnaire (EDE-A, Fairburn et al 2014, which can be adapted for parent-report by substituting "your child" for "you" (Lydecker & Grilo 2017)); b) screening for Avoidant Restrictive Food Intake Disorder (ARFID) using a questionnaire that combines the PARDI-AR-Q (Bryant-Waugh et al 2019 - based on the Pica, ARFID, and Rumination Disorder Interview, PARDI), the ARFID-BS (ARFID brief screener, Dinkler et al 2021), and the NIAS (Nine Item ARFID screen, Zickgraf et al 2018).

The questionnaires will be sent to the research participants prior to the home visit via an online link [REDCap], and will contain a consent procedure.

#### Interview-assessed child psychopathology:

- The Child and Adolescent Psychiatric Assessment (P-CAPA; Angold et al, 1995): will be conducted with the main-caregiver. The CAPA (duration 2-3 hours) provides DSM-IV and ICD-10 diagnoses of all behavioural and psychiatric problems (including detailed assessment of psychotic symptoms), except autism. A child self-report version of the CAPA (C-CAPA) will be used with the children to ascertain psychotic symptoms, mood and anxiety symptoms
- Structured interview for Prodromal Symptoms (SIPS; Miller et al., 2002): conducted with older children to obtain information on prodromal psychosis symptoms.
- Autism Diagnostic Interview–Revised (ADI-R; Rutter et al., 2003): will be conducted where screening by SCQ is positive (duration 1-2 hours). If probands screen positive for autism, in combination with the ADI-R interview conducted with the parents, we will offer the parent the possibility to conduct an observational assessment of the child, to establish autism, using the Autism Diagnostic Observation Schedule (ADOS; Lord et al., 1989). The ADOS is a semi-structured, standardised assessment of communication, social interaction and play. It provides a series of standardised contexts in which the child's social, communication and repetitive, stereotyped behaviours can be observed. Standardised toys and activities are used to present opportunities for social and communicative interaction with the examiner.
- Where appropriate, an interview section [completed via parent and/or child self-report depending on clinical context and child's verbal ability] about eating disorders will be conducted using the Eating Disorder Examination Child version (Bryant-Waugh et al 1996) and the PARDI (Bryant-Waugh et al 2019, The Pica, ARFID (Avoidant Restrictive Food Intake Disorder), and Rumination Disorder Interview).

#### Interview-assessed own and partner psychopathology:

- The 'Family Structure and Function' section of the CAPA will be conducted with the primary caretaker regarding any psychiatric problems faced by themselves and the second caretaker, if applicable. This section provides DSM-IV and ICD-10 diagnoses of the following

psychopathology: depression, anxiety, panic disorders, eating disorders, drug or alcohol use and psychosis. Where appropriate, additional information on eating disorders may be assessed using adult self-report questionnaires (the Eating Disorder Examination Questionnaire (Fairburn et al 2014) and the PARDI-AR-Q (Bryant-Waugh et al 2019)).

### Neurocognitive assessment

Children's' IQ will be assessed using the Wechsler Abbreviated Scale of Intelligence (WASI; Wechsler et al, 1999) and the Computerised Neurocognitive Battery (CNB; Moore et al., 2015) to assess cognition.

### Wechsler Abbreviated Scale of Intelligence (WASI)

**This is an individually administered intelligence test suitable for individuals aged 6-89.** The WASI comprises four subtests (vocabulary, block design, similarities and matrix reasoning) and provides the following intelligence quotient (IQ) scores:

- **Verbal IQ score** - a measure of acquired knowledge, verbal reasoning, and attention to verbal information.
- **Performance IQ scores** – a measure of fluid reasoning, spatial processing, attentiveness to detail and visual-motor integration.
- **Full Scale IQ score** - the overall estimate of an individual's general level of intellectual functioning.

### Computerised Neurocognitive Battery (CNB)

The tests of the CNB measure accuracy and speed of performance and response time, allowing assessment of processing efficiency. The areas of cognition included are: executive-control, episodic memory, complex cognition, social cognition and sensorimotor skills.

The following domains will be assessed with child appropriate versions:

- Abstraction and mental flexibility (ABF)
- Penn Conditional Exclusion Test (PCET), which is a measure of abstraction and concept formation. Subjects decide which of 4 objects does not belong with the other 3, based on one of three sorting principles, which change and feedback is used (4 min)
- Attention (ATT): The Penn Continuous Performance Test (PCPT). Participants respond to a set of 7-segment displays whenever they form a digit or letter (5 min)
- Working Memory (WM): The Letter N-back Test displays sequences of uppercase letters with a stimulus duration of 500 ms (ISI 2,500 ms.) In the 0-back condition, participants respond to a single target (i.e., X). In the 1-back condition they respond if the letter is identical to that preceding it. In the 2-back condition, they respond if the letter is identical to that presented two trials back (9 min)
- Verbal Memory (VMEM): The Penn Word Memory Test presents 20 target words that are then mixed with 20 distractors equated for frequency, length, concreteness and low imageability (3 min)
- Face Memory (FMEM): The Penn Face Memory Test presents 20 digitized faces that are then mixed with 20 distractors equated for age, gender and ethnicity (4 min)
- Spatial Memory (SMEM): The Visual Object Learning Test (VOLT) uses Euclidean shapes as stimuli with the same paradigm as the word and face (2 min)
- Language and Analogical Reasoning (LAN): The Penn Verbal Reasoning Test consists of verbal analogy problems (3 min)
- Spatial Processing (SPA): Penn Line Orientation Test (PLOT) presents two lines at an angle, and participants click on a button that makes one line rotate until it has the same angle as the other (5 min)

- Emotion Processing (EMO): Facial displays of 4 emotions (Happy, Sad, Anger, Fear) and Neutral faces, 8 each, are presented and the subject identifies the emotion in a multiple-choice format. The facial stimuli are balanced for gender, age, and ethnicity (2 min)
- Sensory-motor Processing Speed (S-M): The task requires moving the mouse and clicking on a green square that disappears after the click. The square gets increasingly small and appears in unpredictable locations (2 min).
- Motor Speed (MOTOR): In the Computerized Finger-Tapping Test, participants tap the spacebar as many times as they can in 5 seconds. Three trials each alternate between dominant and non-dominant hands. (4 min).

#### Teacher reports:

- Teachers will be asked to complete a consent form agreeing to complete a questionnaire about their pupils if the participant agrees that the teacher can be approached. We provide a consent form for teachers. Once agreed teachers are asked to complete a brief teacher version of the Strengths and Difficulties questionnaire (SDQ) and further information on child development specifically suited for cognitively impaired children with the Developmental Behaviour Checklist (DBC).

#### Body measurements

We will measure height, weight and head circumference of children and their sibling(s) (if present). Height will be measured using a height measure. Weight will be measured using scales. Head circumference will be measured using a cloth tape. Measurements will be collected using standardized procedures to ensure measurement technique is consistent

#### Biological Samples

Blood/Saliva: We will take 4 EDTA tubes of blood (approximately 40ml) from each participant (proband, sibling, and parents) using venepuncture, if this is not possible, we can take a saliva sample using an Oragene saliva collection tube. Some of the probands may find both these procedures difficult and so we offer an option of a saliva swab. This method will be used only with participants who will struggle with either the venepuncture or saliva collection tube.

Hair root samples (on a subset of cohort): Samples of hair-root keratinocytes will be taken from the children with CNVs and their siblings where possible. We would pluck a few hairs from the scalp so that hair root is sampled from which keratinocytes can be collected at the base of the follicle. Prior to doing this, we shall wash a small area of scalp at the back of the neck with a disinfectant solution (HiBiSCRUB; chlorhexidine gluconate 4% w/v), then the area will be rinsed thoroughly with saltwater, a few hairs will then be plucked using sterile forceps. Once the samples are collected, they shall be placed directly into a cell preservative containing an antibiotic to prevent bacteria growing. This procedure should cause only minor discomfort; however, due to the nature of our sample we are aware that some children may be uncomfortable with this. If so, samples will not be collected.

#### **COVID-19 Pandemic adjustments to Face-to-Face assessments – Online Assessment**

Our face-to-face assessment protocol has had to be adapted to allow the study to continue during the COVID-19 pandemic. Most measures have now been implemented online and we will be able to conduct our interviews using Microsoft teams, Cardiff Enterprise Zoom or by phone, depending on the preference of the participants (see ref 12 for data security measures). Biological sample collection, however, would need to take place at another time, when it is safe again to see families face to face.

We will offer a reduced selection of the above measures to our participants whom we now cannot visit at their homes. This will able us to maintain contact our cohort keeping us connected during

these times where face to face research is restricted. The CAPA interview and questionnaire pack are adaptable to being used online. Saliva sample collection may continue via remote contact, and we will collect blood samples at a later date once restrictions have been lifted.

For other assessments that would usually be included in the usual face-to-face protocol but cannot be completed remotely, participants will be asked if we can visit them at a future date to complete these assessments. If this is impossible we will offer the participants the option to have their face-to-face assessments conducted at Cardiff University in the clinic at the Hadyn Ellis Building.

#### **Avoiding assessment duplication between workstreams 1 & 2:**

We are aware that the online and face-to-face protocols include some potential duplication of assessment procedures. Data collection for both workstreams will be conducted based on information from a centralised database. The decision tree about data collection is based on RedCap. Branching logic within RedCap will ensure that participants who wish to take part in both workstreams 1 and 2 are not asked to complete the same assessment twice.

### **5.6 Study Duration**

IMAGINE-2 was funded for 54 months and was due to end in December 2024. Due to the coronavirus pandemic the timeline of the study has started later and will probably extend until December 2025.

### **5.7 Discontinuation/Withdrawal of Participants from Study**

Every participant has the right to withdraw from the study at any time; we will remove participants from the study at any time if it becomes necessary for any reason. Withdrawal from the study will not result in exclusion of the data for that participant from analysis. Participants will be offered two levels of withdrawal options:

*“No further contact”*: This means that IMAGINE-ID would no longer contact the participant, but would retain permission to keep and use information and/or samples provided previously, and to obtain and use data from the participant's health (Hospital Episode Statistics) and school (National Pupil Database) records.

*“No further use”*: This means that, in addition to no longer contacting the participant or obtaining further information, any information (and samples) collected previously would no longer be available to researchers. IMAGINE-ID would destroy the participant's samples (although it may not be possible to trace all distributed sample remnants) and would only hold participant contact information for archival audit purposes. Such a withdrawal would prevent information from contributing to further analyses. However, it is not possible to remove previously gathered data (IMAGINE-1) from public databases (the UK Data Archive), or data that have been shared with other researchers outside our organization.

The reason for withdrawal will be recorded in the CRF.

### **5.8 Definition of End of Study**

The end of study is the date of the last assessment follow up of the last participant (e.g. wave 5).

## 6 Statistics

### 6.1 Statistical methods to be employed (plan of analysis)

#### **Workstream 1:**

The analytic framework we will use in Workstream 1 aims to detect risk and protective factors; we seek to identify variables (at the biological, psychological and social level) that are associated with better or worse outcomes, using a two-step analytic strategy.

*As a first step*, our analysis in Workstream 1 would define groups characterized by distinct developmental trajectories of generalized emotional/behavioural problems defined by the total SDQ score at each time-point. Follow-up data are to be sought for all people ( $n \sim 3000$ ) recruited in IMAGINE-1, for whom we have baseline measures. [The differences of the wellbeing and mental health state of the IMAGINE and control cohorts will be investigated using the IMAGINE-1 research \(DAWBA/SDQ/ABAS\) and MHCYP data, considering the fixed effects of age, gender, ethnicity and index of multiple deprivation.](#) All analyses will be performed in RStudio and Mplus.

Following an analytic strategy that was employed by a comparable longitudinal study of behavioural adaptation with the SDQ we will describe trajectories of internalizing and externalizing problems and adaptive functioning over the period of follow-up by fitting a parallel-process growth mixture model (GMM). The growth parameters, i.e., the slope and intercept, will be estimated for each of the repeatedly measured variables (SDQ/ABAS). A latent class variable will be estimated, defined by the growth parameters of the parallel processes.

We will estimate models with a small number of potential classes and compare model fit with four commonly used goodness of fit indices:

- (1) the Bayesian information criterion (BIC);
- (2) the sample size-adjusted BIC (SSA-BIC);
- (3) the Akaike information criterion (AIC);
- (4) the entropy of each model.

Lower BIC, AIC and SSA-BIC values indicate better fit to the data. Entropy ranges from 0 to 1, with higher values indicating that the latent classes are clearly distinguishable (values  $\geq 0.80$  are considered adequate). Solutions with extremely small classes ( $\leq 1\%$  of the sample) or with several small classes ( $< 2\%$  of the sample) will be disregarded.

The GMM will be carried out using the maximum likelihood with robust standard errors estimator, which is robust to non-normality in the data. Full information maximum likelihood (FIML) will be used to accommodate missing data in problem behaviour and adaptive functioning. Under the assumption that the data are missing at random (MAR), FIML can estimate parameters using any available information that is contained in the dataset. FIML is also considered superior to other techniques used to handle missing data in terms of bias and the sampling variability of the parameter estimates produced. To avoid model convergence to local maxima, we may increase the number of random starts. We will follow a classic three-step analysis whereby, upon selection of the optimal latent class model, the latent class variable is extracted and used as an observed variable for further testing. We note that one-step approaches whereby the latent class variable is extracted and examined in terms of its associations with covariates and outcomes in the same analytical step are frequently used, but they can be problematic when examining a large number of covariates.

In addition, simulations have shown that in models with high entropy values, the covariates do not influence class assignment to a large extent. Upon examination of the distribution of the covariates

across the extracted classes, we will run regression models to measure the associations between class membership and outcomes at the final follow-up assessment (e.g. worsened/improved/no change). We will use linear, logistic, ordered logistic and multinomial regression models, depending on the scale of measurement of each outcome. Potential moderators of risk include: environmental variables (Index of Multiple Deprivation, ethnicity, parental education); biological variables including age, sex, medical history (including treatments for neurodevelopmental disorders); and genotypic variables such as whether the genetic anomaly was inherited or *de novo*, and mutational burden (e.g. sum of the lengths of CNVs containing neurodevelopmental genes).

From the HES data, the control cohort will be matched to the IMAGINE-2 study group in age range, gender, ethnicity and index of multiple deprivations. Patterns of healthcare usage will be identified and their association with developmental trajectories of mental health will be evaluated, revealing any differences between cohorts. Incidence rates of the hospital episodes will be derived by age (from birth) and analysed using negative binomial or Poisson regression, allowing for a random intercept per child to account for longitudinal nature of the HES data.

We will identify clusters of similar usage and test the extent to which the composition of clusters is influenced by genetic, familial and environmental factors in IMAGINE-2 cohort. They also will be grouped according to how they interact with healthcare facilities and their healthcare use trajectories using group based multi-trajectory model / sequence analysis. Mixed model regression and latent class analysis will be employed to compare domain-specific trajectories between the IMAGINE-2 and control cohorts. Specific patterns of NHS facility usage associated with the trajectories will be determined, accounting for child's age, sex, demographic variables (including age of genetic diagnosis) and health characteristics (genetic condition, medical or surgical interventions, mental health problems). As a result of these analyses, points of strength and weakness in hospital services can be identified in both cohorts.

At the second step of our analysis, we will be examining predictors of onset of events, primarily new psychiatric disorders, based both on intermediate measures (SDQ/ABAS-3) and on diagnostic data from the DAWBA administered at the 5-year follow-up. An analytic framework suitable for predictions such as this, which incorporate state (diagnosis at outcome) and trait (the intermediate) risk factors, including genetic risk factors, has recently been described. We are particularly interested in studying transition to psychosis, as many of the genetic anomalies identified by IMAGINE-1 convey an enhanced risk in late adolescence and early adulthood (up to 21% incidence between 14-19 years). Our approach would test predictions based on the three step analysis described in step one of this analytic plan, using the latent classes in a logistic regression for a distal binary outcome (e.g. psychosis/no psychosis). The comparison of IMAGINE-2 cohort with the MHCYP data enables the identification of differences in vulnerability to mental health conditions.

In a separate set of analyses, we are planning to make use of the substantial free-text commentaries by families in the DAWBA interviews. We will employ natural language processing (e.g., Sentiment analysis and support vector clustering) to derive new measures of clinical severity, in collaboration with our collaborator at the Institute of Health Informatics (UCL), [name]. Preliminary work to establish proof of principle has proved promising.

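### Workstream 1 analyses the extracted trajectory class as if it were observed without error, so class associations are biased, usually but not always toward the null

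*Protocol*

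**What the plan says.** Protocol section 6.1, Workstream 1, first step, fits a parallel-process growth mixture model to the SDQ and ABAS. One model is chosen from the BIC, sample-size-adjusted BIC, AIC and entropy. On entropy the text says "Entropy ranges from 0 to 1, with higher values indicating that the latent classes are clearly distinguishable" and describes 0.80 or more as adequate. Solutions are discarded only for class size: a class of 1% or less, or several below 2%.

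The protocol then commits to a classic three-step analysis: "upon selection of the optimal latent class model, the latent class variable is extracted and used as an observed variable for further testing". It sets this against one-step estimation only, of which it says "they can be problematic when examining a large number of covariates", and adds that "simulations have shown that in models with high entropy values, the covariates do not influence class assignment to a large extent".

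Three uses of the class follow:
- Covariates are compared across the extracted classes.
- For final outcomes, "we will run regression models to measure the associations between class membership and outcomes at the final follow-up assessment". The example given is whether the child worsened, improved or did not change.
- In the second step, predictions are tested by "using the latent classes in a logistic regression for a distal binary outcome (e.g. psychosis/no psychosis").

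Section 6.1 mentions no correction for classification error, no weighting by posterior probability and no sensitivity analysis for this step. It names RStudio and Mplus as software.

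**The concern.** A latent class is estimated, and some children are put in the wrong one. If the assigned class is entered in a regression as though observed, each assigned group is a mixture of true classes and its contrast with the others is distorted. The standard error also treats the assignment as known.

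The protocol's defence does not meet this. Its two arguments, many covariates and high entropy, bear on whether covariates would shift class formation in a one-step model. Neither concerns error in a class that has already been assigned. Nor is this a detail left for the SAP: the protocol names the uncorrected method and argues for it.

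Workstream 1 exists to find risk and protective factors, and its moderator and psychosis analyses all pass through this step. A real risk class may look weaker than it is, and a class with no excess risk may appear to have some.

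**Working it through.** The protocol states no effect size, power or precision for these analyses, so there is no figure to reproduce. Class sizes, separation and true effects are not given either, and **all of them below are assumptions**. From the protocol come the 0.80 entropy level and the incidence of up to 21% for psychosis, used here only as an illustrative upper risk.

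**Set-up.** Classes are normal with unit variance, means a distance *s* apart, with *s* tuned to a target entropy. Relative entropy is E = 1 − Σᵢ Σₖ(−pᵢₖ ln pᵢₖ)/(n ln K). Each child goes to the most likely class. The protocol says only that the class is extracted, so modal assignment is also an assumption. With two classes the cut lies at s/2 + ln(π₁/π₂)/s.

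**Two classes, 80/20, entropy 0.80.** Outcome risks are 5% and 15%, so the true OR is (0.15/0.85)/(0.05/0.95) = 3.35.
- s = 2.90; cut = 1.45 + 1.386/2.90 = 1.93.
- Correctly placed: 97.3% of the large class, 83.5% of the small one.
- True small-class share among those assigned to the small class: 0.20×0.835/(0.20×0.835 + 0.80×0.027) ≈ 0.886. Among those assigned to the large class: 0.20×0.165/(0.20×0.165 + 0.80×0.973) ≈ 0.041.
- Risks by assigned class: 0.05 + 0.10×0.886 = 0.1386 and 0.05 + 0.10×0.041 = 0.0541.
- Naive OR = (0.1386/0.8614)/(0.0541/0.9459) = 2.81. The log-OR is about 86% of truth. Simulation gave 2.85 (87%).

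**Two classes, 95/5, entropy 0.80, same risks.** Here s = 1.67 and only 18% of the small class is correctly placed. The shares are 0.666 and 0.042, the risks 0.1166 and 0.0542, and the naive OR 2.30 (69%). Simulations gave 2.24 to 2.36 (67 to 71%). With classes this unequal, entropy is already 1 − 0.199/0.693 = 0.71 with no separation at all, so 0.80 says little about how well the small class is identified.

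**Three classes, 60/25/15, true ORs 3 and 5, entropy 0.80.** Simulations gave 2.5 and 4.0 in one layout of the class means (84 to 86%), and about 2.6 and 4.4 in another: ln 2.6/ln 3 = 0.87 and ln 4.4/ln 5 = 0.92.

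**Higher entropy, naive log-OR as a share of truth.**

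| Classes | 0.80 | 0.90 | 0.95 |
|---|---|---|---|
| 80/20 | about 86% | 93% | 97% |
| 95/5 | about 69% | 84% | 91% |

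**Four ordered classes, 55/20/15/10, entropy 0.80.** Risks are 5%, 5%, 5% and 21%, so the true ORs against the first class are 1, 1 and 5.05.
- Those assigned to the third class include 8.1% who belong to the fourth. Their risk is 0.05 + 0.16×0.081 = 0.0630, and the naive OR is (0.0630/0.9370)/(0.05/0.95) = 1.28. Simulations gave 1.27 and 1.29.
- Those assigned to the fourth class are 89.3% correct. Their risk is 0.1929 and the OR 4.54 (simulation 4.49), so the log-OR is about 93% of truth.
- For a covariate predicting class, true log-ORs of 0, 0.80 and 0 became 0.06, 0.65 and 0.08.

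**Effect of a correction.** Weights from the inverted classification-error matrix (BCH type) returned 3.40 for 80/20 and 3.46 for 95/5 (truth 3.35), and 0.99, 1.02 and 4.98 for the four classes (truth 1, 1, 5.05).

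**Outcome sharing measurement with the class.** Two classes 80/20, entropy 0.80, true mean difference 0.50:

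| Within-class correlation of outcome with class indicator | Naive | Corrected |
|---|---|---|
| 0 | 0.42 | 0.50 |
| 0.2 | 0.55 | 0.65 |
| 0.4 | 0.68 | 0.81 |

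In the first row, naive = 0.50×(0.886 − 0.041) = 0.42. In the other rows the naive estimate is too large, and the correction moves it further from the truth.

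**The case against.** The best defence is that the protocol treats 0.80 as its mark of adequate entropy, and that the bias is modest when classes are sizeable and well separated: about 7% of the log-OR at 0.90 and 3% at 0.95 in the 80/20 case. That stands. But 0.80 is not a stated condition for using the classes, and small classes above the size limits can be kept.

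A reader might infer that every association is shrunk toward the null. The plan does not support that. The direction is assured only for two classes with error unrelated to the outcome. With more classes a null class can borrow its neighbour's effect. A final outcome of worsened, improved or unchanged, if scored on the SDQ or ABAS, can be inflated.

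A reader might also infer that results would not be comparable between models of different entropy. Section 6.1 selects one model and tests only that one, so this harm does not arise.

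Finally, a standard correction is not a universal cure. It assumes the outcome is independent of the class indicators given class. Where that fails it makes matters worse, as the last table shows. This limits the fix but does not defend the uncorrected step.

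**Conclusion.** The point holds in limited form. The protocol specifies a step that ignores classification error, and its stated reasons do not address that error. At entropy 0.80, under the assumed two- and three-class structures, the naive log-OR is roughly 67 to 92% of the truth, lowest for a 5% class. With four classes the raised class keeps about 93%, while a null neighbour shows an OR near 1.3. Standard errors are also too optimistic, by an amount not calculated here.

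All these sizes rest on assumed class proportions, separation, risks and modal assignment. They show what entropy 0.80 permits, not what this cohort will show. Whether the final change outcome shares measurement with the classes depends on how it is scored, which the protocol does not say. The SAP was not at hand; if it already specifies a corrected step, the protocol sentence should be brought into line with it.

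**What to change.** Keep the three-step sequence and amend the sentence in section 6.1 along these lines:

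- **Primary analysis:** carry the classification-error matrix into step three. Use ML three-step for predictors of class, and BCH or ML three-step for distal outcomes such as DAWBA diagnoses or psychosis.
- **Sensitivity analysis:** naive class assignment, reported beside the primary result with the entropy and the per-class classification rates.
- **Outcomes scored on the SDQ or ABAS:** do not rely on the correction. Use an outcome that did not help form the classes, or report the association as descriptive. State how the worsened/improved/unchanged outcome is scored.

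That Mplus offers these methods is general methods knowledge; the protocol only names the software.

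The cost is a short protocol amendment, modest syntax for each type of regression planned, wider intervals and some extra model-checking. BCH can be unstable at low entropy, in which case ML three-step is the alternative. The DAWBA is also parent-reported, so independence from the SDQ given class is more plausible there but still worth checking. Data collection does not change.
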